### C8. Statistical Considerations:

Power analysis was completed for the primary outcome of percentage reduction in average cigarettes per day smoked in the last week of sampling, and based on data from [name] previous e-cigarette sampling trial during which participants received a low power (1st Gen) device with one of two nicotine concentrations (low or high). We hypothesize that the impact of nicotine concentration on CPD reduction would be similar here for the low power groups and that the effect would be reversed, but of similar size, in the high-power groups (Figure 3a). The hypothesized interaction is shown during the last week of sampling for simplicity in Figure 3b, specifically that for the low power setting, a higher concentration will produce a larger decrease in cigarettes per day than the low concentration, but for the high-power setting, a higher concentration will produce a smaller decrease in cigarettes per day than the low concentration. We use the methods described by Fleiss for estimating power for interaction effects. As he notes, the variance of an interaction effect is four times that of the corresponding main effect. Thus, even large effects require large sample sizes to yield adequate power. In this case, a sample size of 40 participants / group will provide 80% power to detect an interaction among the two factors with a 0.050 significance level, assuming that the common standard deviation is 38% reduction in CPD, as was the case in [name] trial. However, we inflate this sample size by 10%, accounting for attrition over time, and thus aim to **recruit 45 participants randomized per group (total N=180)**.

For aims 1 and 2, we will assess the impact of concentration and power on each outcome across time using a generalized estimating equation that includes concentration, power, sampling week (time), and their interactions. Hypothesis 1 will focus on percentage reduction in CPD, Hypothesis 2 will focus on e-cigarette uptake (puffs per day), and Hypothesis 3 will focus on complementary measures of preference/demand, all of which are captured at Visit 4. Outcomes that are skewed (e.g., demand parameters, urinary cotinine) will be log transformed. It is possible that reductions in CPD will be bimodal in the last week of sampling, reflecting a subset of participants who may quit smoking during the trial. In this case, we would conduct a Chi-square test on the proportion of participants who reduce their smoking by at least 50%. Exploratory analyses on age will be conducted by adding age to the model. [name] (co-mentor) will be meeting with [name] monthly for training in these analyses, and will also be available to assist with the eventual power analysis for the R01 submission based on these data.

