**Specific Aim 1:** To understand the impact of nicotine concentration and device power on cigarette smoking (cigarettes smoked per day; CPD) and smoke exposure (expired breath carbon monoxide; CO). Hyp1: There will be an interaction such that a higher (vs. lower) nicotine concentration will produce greater reductions in CPD and CO when device power is low, and a lower nicotine concentration will produce greater reductions in CPD and CO when device power is high. Hyp2: Parallel analyses will test the main and interactive effects of nicotine concentration and device power on e-cigarette use (hypothesizing more puffs per day).

**Specific Aim 2:** To understand the impact of nicotine concentration and device power on relative reinforcement value (choices to smoke versus use an e-cigarette in a lab-based preference task, demand for each product on a hypothetical purchase task). Hyp3: There will be a similar interaction such that a higher nicotine concentration will result in fewer choices to smoke a low power device, and a lower nicotine concentration will result in fewer choices to smoke in a high-power device.

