**C5b. Sampling (Visits 2-4):** We considered a longer sampling period but our experience in prior sampling studies is that 3 weeks is sufficient to acclimate (77). Over the three-week sampling period, participants will complete daily electronic diaries cataloging their cigarette and e-cigarette use. Each morning, participants will receive an e-mail or text message link to complete their diary. The diary will assess tobacco use the previous day including cigarette smoking, number of e-cigarette puffs per day, quit attempts, and craving. This electronic daily diary is currently being used in [name] R01 and [name] pilot study, with compliance > 90%. Participants will attend weekly in-person visits where they will complete assessments regarding tobacco use, craving, dependence, product perceptions, as well as provide expired carbon monoxide samples. Urine samples for cotinine analysis will be provided at randomization and at the end of sampling. Research staff will conduct routine device maintenance at these visits. At the end of the sampling period (Visit 4), participants will return their e-cigarette device and e-liquid, and complete the preference assessment again.

**C5d. Follow-up (Visit 5):** Participants will return to the lab one month following the end of the study to assess their cigarette smoking, e-cigarette use, e-cigarette purchases, and provide expired breath carbon monoxide.

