**C7c. Measures of tobacco use:** Daily cigarette use will be captured using an electronic daily diary in which participants report the number of cigarettes they smoked (< 2 min/day). We will collect expired breath carbon monoxide at each weekly visit, which provides an objective measure of recent exposure to smoke, but is unaffected by e-cigarette aerosol. During weekly assessments, we will retrieve information about e-cigarette use from the device, using eScribe software described above. The software provides the number of puffs taken each day and the average puff duration. Within weekly lab visits, participants will retrospectively report these outcomes via timeline followback.

**C7d. Measures of Nicotine Delivery:** Participants will provide urine samples for testing of cotinine (primary metabolite of nicotine) within our Departmental lab. We will not be able to discriminate the source of nicotine

(cigarette vs. e-cigarette), but will be able to test whether overall nicotine exposure has increased or decreased from baseline. We will also measure the quantity of nicotine liquid that participants use by weighing the e-liquid bottles at distribution and at each visit, which combined with the concentration provides some information about nicotine intake from the assigned e-cigarette. We will also assess subjective assessments of nicotine effects including withdrawal (MNWS), and craving to smoke (QSU).

**C7e. Measures of Sensorimotor Cues:** Because e-cigarettes are relatively new products, there are no validated measures to assess reinforcement from sensorimotor cues. In consultation with [name] (co-mentor) we will include items that assess participant satisfaction with throat hit, aerosol volume, aerosol temperature, and flavor. These items will be added to a modified version of the mCEQ, which will assess reward and satisfaction from both cigarettes and e-cigarettes.

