##### 1.2 Study Procedures, Materials, and Potential Risks:

###### Study Procedures:

Participants will be screened over the phone to determine initial eligibility. Alternatively, participants may complete a redcap survey to determine initial eligibility. Participants will see a script that briefly explains the study. Once participants have been determined to be initially eligible, they will be invited to participate in the consent process. The consent process will take place via one of the following modalities: 1) Remote electronic

[figure not shown]

Figure 3a: Hypothetical Changes in CPD over sampling

[figure not shown]

Figure 3b: Impact on reduction in CPD

consent (e-consent) via REDCap facilitated with a discussion over the phone, 2) Remote consent via doxy.me, or 3) in-person consent (in-person visit at start of Visit 1). During the COVID-19 restrictions, all consenting will be done remotely (not in-person). We have built in the option for electronic consent to reduce the length of the first in-person visit and while still providing ample time for the consent process. Consented participants will be asked to attend an in-person screening session. Participants will be asked to provide a carbon monoxide sample to confirm smoking status, and women will provide a urine sample for pregnancy testing. Participants will then complete a series of interview-administered and participant-administered questionnaires that assess brief medical history, tobacco use history including prior and current e-cigarette and cigarette use, current use of smoking cessation products, and demographics. After all questionnaires have been completed, study staff will determine participant eligibility.

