Participants who are eligible will then provide a urine sample for cotinine analysis and complete additional baseline questionnaires including measures of nicotine dependence. Participants will be randomized to one of four groups as described above and will have the opportunity to sample their usual brand cigarette and their assigned e-cigarette and e-liquid for the first time. After sampling each product, participants will complete additional questionnaires and complete the preference assessment where they choose between their cigarette and assigned e-cigarette. At the end of Visit 1, participants will receive a one week supply of e-liquid to take home with their assigned e-cigarette, will be enrolled in the daily electronic diary system, and will be provided with instructions for completing diaries.

Participants will return to the lab for three additional weekly visits, and will receive a new supply of e-liquid for each week. At each visit, we will assess tobacco use during the prior week, participants will provide an expired breath carbon monoxide sample, adverse events will be assessed, and participants will complete questionnaires about their assigned e-cigarette and e-liquid. At the fourth and final weekly visit, participants will complete the sampling and preference assessment again, providing another urine sample for cotinine testing, and return any unused study product.

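### The GEE names no Visit 1 value of CO or urinary cotinine as a covariate, although both are collected before randomization, so some precision on these supporting outcomes may be given up

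*Combined protocol and SAP*

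**What the plan says.** C8 and the Statistical Analysis Plan both specify, for Aims 1 and 2, a "generalized estimating equation that includes concentration, power, sampling week (time), and their interactions". The only other covariates mentioned are age (exploratory), flavor (only if needed, in C1) and gender (examined separately, in the Statistical Analysis Plan).

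Both biomarkers are in hand before allocation. Section 1.2, Study Procedures, has CO taken at screening: "Participants will be asked to provide a carbon monoxide sample to confirm smoking status". It then continues: "Participants who are eligible will then provide a urine sample for cotinine analysis and complete additional baseline questionnaires". Randomization is described after these steps.

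At follow-up, C7c states: "We will collect expired breath carbon monoxide at each weekly visit". For cotinine, C5b states: "Urine samples for cotinine analysis will be provided at randomization and at the end of sampling".

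The plan suggests a comparison with baseline without defining it. Specific Aim 1 predicts that a higher concentration "will produce greater reductions in CPD and CO when device power is low". C7d says of cotinine that the investigators "will be able to test whether overall nicotine exposure has increased or decreased from baseline". On scale, C8 says: "Outcomes that are skewed (e.g., demand parameters, urinary cotinine) will be log transformed". The response for CO is not defined further.

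**The concern.** A pre-randomization measurement of the outcome is usually its best single predictor. Used as a covariate, it removes between-participant variation from the treatment contrast at no data cost. The listed terms do not include it.

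CO stands beside CPD in Aim 1, and the Specific Aims rely on biomarkers to corroborate self-report. The hypothesis is an interaction, and C8 itself notes that an interaction has four times the variance of the corresponding main effect. The sample size was set for CPD alone, so CO and cotinine have no power allowance of their own. At stake is the width of the confidence interval on the CO and cotinine interactions, and nothing beyond that.

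**Working it through.** **The plan's own figure.** C8 states 40 per group for 80% power on percentage CPD reduction, with SD 38. The effect size is shown only in a figure, so the power cannot be recomputed. Back-solving two-sided gives 2.80 × 38 × √(4/40) = 33.7 points for the interaction. The attrition step reproduces: 40/(1 − 0.10) = 44.4, so 45 per group and 180 in total. None of this depends on how CO or cotinine is modelled.

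**Basic formulas.** Take one follow-up value, equal SDs at baseline and follow-up, and baseline-to-follow-up correlation r. The variance of the interaction, relative to follow-up levels, is:
- levels: 1
- change from baseline: 2(1 − r)
- adjusted for baseline: 1 − r²

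So adjusted/levels = 1 − r² (0.91, 0.75, 0.51 at r = 0.3, 0.5, 0.7) and adjusted/change = (1 + r)/2 (0.65, 0.75, 0.85). Simulation with 40 per cell gave 0.92, 0.77, 0.54 and 0.65, 0.75, 0.84.

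**Visit 1 as a time level.** With all interactions included, a GEE on Visit 1 plus one follow-up returned an interaction-by-time coefficient of −0.17936. The change-score contrast on the same simulated data was also −0.17936. This reading is therefore the change analysis.

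**CO with the entry rule and unequal SDs.** From the documents: the CO > 8 ppm entry rule (C3). Assumed, because the documents give no value: log CO normal before the entry rule with SD 0.5, median 12 or 18 ppm, r = 0.3, 0.5, 0.7 before the rule, and a follow-up to baseline SD ratio k of 1, 1.5 or 2.

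The rule leaves a share v of the baseline variance. With a = (ln 8 − ln median)/0.5 and λ = φ(a)/(1 − Φ(a)), v = 1 + aλ − λ².
- Median 12: a = −0.811, λ = 0.363, v = 0.574
- Median 18: a = −1.622, λ = 0.113, v = 0.804

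With slope b = rk and residual E = k²(1 − r²), the variances in units of the baseline variance before the rule are:
- levels: b²v + E
- change: (b − 1)²v + E
- adjusted: E

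Example at median 12, r = 0.5. For k = 1, E = 0.75, and levels and change are both 0.25 × 0.574 + 0.75 = 0.894; 0.75/0.894 = 0.839, a 16% reduction. For k = 1.5, b = 0.75 and E = 1.6875, and change is 0.0625 × 0.574 + 1.6875 = 1.723; 1.6875/1.723 = 0.979, a 2% reduction.

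Reduction in interaction variance from adjustment, against the better / the worse of levels and change:

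| k | r | median 12 | median 18 |
|---|---|---|---|
| 1 | 0.3 | 5% / 24% | 7% / 30% |
| 1 | 0.5 | 16% / 16% | 21% / 21% |
| 1 | 0.7 | 9% / 36% | 12% / 44% |
| 1.5 | 0.3 | 5% / 8% | 7% / 11% |
| 1.5 | 0.5 | 2% / 16% | 3% / 21% |
| 1.5 | 0.7 | 0% / 36% | 0% / 44% |
| 2 | 0.3 | 2% / 5% | 3% / 7% |
| 2 | 0.5 | 0% / 16% | 0% / 21% |
| 2 | 0.7 | 4% / 36% | 6% / 44% |

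The loss from using change is proportional to (b − 1)² and vanishes when the slope is 1. The loss from using levels is proportional to b² and vanishes only when r is 0. Adjustment is never worse than either in large samples. These are single-visit calculations; the plan's model spans several visits.

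**The case against.** The strongest reply has four parts.

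- **The size is uncertain.** Spread may well rise once product is supplied: C8 itself anticipates bimodal CPD reductions with some quitters, and the entry rule narrows baseline. If follow-up log SD is 1.5 to 2 times baseline, the gain over the better scale is only about 0-7%. The wording in Specific Aim 1 and C7d favours change, which is often the better scale in those cases. This stands, and both ranges are reported for that reason.
- **The plan is silent, not wrong.** A reader might infer that the trial ignores baseline CO and cotinine altogether. The documents do not support that: both sections imply a comparison with Visit 1. What is missing is how baseline enters. A model holding the groups equal at baseline would avoid the loss, but none is described, and each reading that fits the listed terms is at best equal to adjustment.
- **Cotinine is less certain.** It is in neither aim, and C8 mentions it only as an example for log transformation. C5b gives two samples, while the cotinine row of Table 1, as extracted, carries three marks in columns that cannot be read reliably. This stands; the cotinine part is conditional, and the fix must not discard an intermediate sample.
- **Little follows for the trial.** True, since these are supporting outcomes. But the change is nearly free, and it settles a choice otherwise left until the data are seen.

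**Conclusion.** The point holds as a minor matter of efficiency. The listed model terms do not include the Visit 1 value of CO or cotinine, and naming it as a covariate is in large samples at least as precise as any unadjusted reading of the plan.

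For CO, the variance reduction against the better unadjusted scale is about 5-21% with equal log SDs (about 3-11% in standard error). It is about 0-7% with follow-up log SD 1.5 to 2 times baseline. Against the worse scale it is larger, up to 44%, and the plan does not say which scale it will use. Every one of these figures rests on assumed correlations, medians and SDs. No separate range is claimed for cotinine.

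A reader might also infer that the comparison is biased or the trial underpowered. Neither follows. Randomization keeps the unadjusted contrast unbiased, the type I error is unaffected, and the sample size and primary outcome concern percentage CPD reduction. No conclusion of the trial is shown to change.

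**What to change.** After the GEE sentence in both C8 and the Statistical Analysis Plan, state that:

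1. The CO model takes the post-baseline sampling visits (Visits 2-4) as responses on one named scale (for example log CO if skewed, with a stated rule for zero readings), with Visit 1 CO on the same scale as a covariate.
2. Any cotinine model takes all post-baseline log cotinine values collected during sampling as responses, with log Visit 1 cotinine as a covariate. That means the end-of-sampling value under C5b, plus any intermediate sample if Table 1 intends one.

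On a fixed scale, adjusted level and adjusted simple change give the same interaction estimate. This does not extend to percentage change, so the CO scale has to be named.

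The cost is one or two sentences and one degree of freedom per model. In a single-visit analysis with 40 per cell, that is one of 160 − 4 = 156 residual degrees of freedom. No new data are needed and the sample size does not change.

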### Protection of res

#### 1. Risks to Human Subjects

##### 1.1 Human Subjects Involvement, Characteristics, and Design:

Current smokers (n=180) will be randomly assigned to one of four research groups in a 2X2 between-subjects design. All participants will receive an e-cigarette and e-liquid to sample over a three-week period. The e-liquid will either have a low or a high nicotine concentration, and the e-cigarette will either have a low or a high-power setting. Group assignment will be double-blind, and 15 participants will be randomized to each group.

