### C3. Participants:

Daily cigarette smokers (n=200) will be recruited from the local community using standard media outlets. We will also submit a Research Data Request to obtain a recruitment report of MUSC patients who potentially meet eligibility criteria. The study team will not cold-contact any patients who have opted out of receiving contact about research or who have met the maximum number of contact attempts at the time of recruitment. We will reach out to these potential participants via MyChart message, text message, phone call, or email no more than three times via any one contact method. Although we anticipate having 180 participants complete the study, here we have increased this sample size to 200 in anticipation of attrition. We will recruit an equal number of young adult (21-30) and older adult smokers (>30) to allow for exploratory analysis on the impact of age. In/exclusion criteria are designed to enroll relatively healthy smokers who predominately use cigarettes and have limited experience with e-cigarettes. Inclusion criteria include a) adults who have been smoking at least five cigarettes daily for the past year (baseline CO > 8ppm), b) rate their interest in using e-cigarettes as >5 on a 0-10 scale, c) have a smartphone that can receive text messages and has access to the internet or has an e-mail account they check daily and d) must be age 21 or older. Exclusion criteria include a) use of tobacco products other than cigarettes, including e-cigarettes, on ten or more days in the past 30 days, b) current use of cessation medications, c) pregnant, trying to become pregnant, or breastfeeding, d) recent history of cardiovascular distress in the last three months (e.g., arrhythmia, heart attack, stroke, uncontrolled hypertension), e) history of a seizure disorder, f) household member currently enrolled in the study.

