#### **C5. Procedures:**

**C5a. Screening, Baseline, and Randomization (Visit 1):** Potential participants will be phone screened for initial eligibility. Alternatively, participants may complete a Redcap survey to determine initial eligibility. Participants will see a script that briefly explains the study. Those meeting criteria will either by consented electronically or consented at an in-person visit. Consented participants will attend an in-person visit where they complete additional baseline measures and provide a urine sample for cotinine analysis. We will provide transportation via a taxi cab company for participants who are eligible, but do not have reliable transportation to in-person visits. All participants will receive an e-cigarette and e-liquid, varying in 2x2 manner on both nicotine concentration (3 vs. 12 mg/ml) and power (20W vs 40W) (n=45cell). Participants will be given instructions

about how to fill and operate their device, similar to what might be conveyed online or in a vape shop. Participants will be told to use the e-cigarette as much as they would like, and that they are not required to use the e-cigarette or to smoke cigarettes, but we request that they do not use any non-study e-cigarettes during this time period (to avoid use of products with different characteristics than those assigned). We are forced to rely on self-report of non-study e-cigarette use, but we do not expect it to be a pervasive problem given that current e-cigarette users are excluded, and because we provide product for free. Both participants and research staff will be blind to assigned nicotine concentration and power settings. At each visit, participants will be provided with a one-week supply of e-liquid such that they could exclusively use the e-cigarette if they choose to do so. Participants will also complete a lab-based preference assessment (described below).

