## Statistical Analysis Plan

Power analysis was completed for the primary outcome of percentage reduction in average cigarettes per day smoked in the last week of sampling, and based on data from [name] previous e-cigarette sampling trial during which participants received a low power (1st Gen) device with one of two nicotine concentrations (low or high) (84). We hypothesize that the impact of nicotine concentration on CPD reduction would be similar here for the low power groups and that the effect would reversed, but of similar size, in the high-power groups. In this case, a sample size of 40 participants / group will provide 80% power to detect an interaction among the two factors with a 0.050 significance level, assuming that the common standard deviation is 38% reduction in CPD, as was the case in [name] trial (84). However, we inflate this sample size by 10%, accounting for attrition over time, and thus aim to **recruit 45 participants randomized per group (total N=180)**.

For aims 1 and 2, we will assess the impact of concentration and power on each outcome across time using a generalized estimating equation that includes concentration, power, sampling week (time), and their interactions. Hypothesis 1 will focus on percentage reduction in CPD, Hypothesis 2 will focus on e-cigarette uptake (puffs per day), and Hypothesis 3 will focus on complementary measures of preference/demand, all of which are captured at Visit 4. Outcomes that are skewed (e.g., demand parameters, urinary cotinine) will be log transformed. It is possible that reductions in CPD will be bimodal in the last week of sampling, reflecting a subset of participants who may quit smoking during the trial. In this case, we would conduct a Chi-square test on the proportion of participants who reduce their smoking by at least 50%. Exploratory analyses on age will be conducted by adding age to the model. As described in the Career Development Plan, [name] (co-mentor) will be meeting with [name] monthly for training in these analyses, and will also be available to assist with any unexpected issues. Gender will be examined separately as a direct or moderating influence on all outcomes.

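### Section 1.1 randomises 15 per group where the rest of the plan has 45, and 180 serves both as the number randomised and as the number completing

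*Combined protocol and SAP*

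**What the plan says.** The sample size appears in five places.

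- **Section 1.1, Human Subjects Involvement, Characteristics, and Design.** It opens with "Current smokers (n=180) will be randomly assigned to one of four research groups in a 2X2 between-subjects design" and ends with "Group assignment will be double-blind, and 15 participants will be randomized to each group".
- **C5a, Screening, Baseline, and Randomization.** The e-cigarette and e-liquid vary "on both nicotine concentration (3 vs. 12 mg/ml) and power (20W vs 40W) (n=45cell").
- **C8, Statistical Considerations, and the Statistical Analysis Plan.** Both state that "a sample size of 40 participants / group will provide 80% power to detect an interaction among the two factors". Both then add 10% for attrition and aim to "recruit 45 participants randomized per group (total N=180").
- **C3, Participants.** "Daily cigarette smokers (n=200) will be recruited from the local community using standard media outlets". It goes on: "Although we anticipate having 180 participants complete the study, here we have increased this sample size to 200 in anticipation of attrition".

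The Abstract and the Specific Aims also give n=180, for smokers who receive the product.

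**The concern.** There are two separate inconsistencies.

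First, section 1.1 contradicts itself: 180 people spread over four groups cannot be 15 per group. This is the section that describes how many people are exposed, so the figure should not be in doubt.

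Second, 180 has two meanings. In C8, the SAP and section 1.1 it is the number randomised; in C3 it is the number who finish. Both can be true only if nobody is lost after randomisation, and C8 and the SAP explicitly plan for loss over time. C3 also does not say whether its 200 recruited are people consented or people randomised.

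Read literally, the number randomised could be 60, 180 or 200, and the number completing about 160 or 180. A reader could not judge whether recruitment and retention met the plan. A literal 15 per group would also leave the interaction test badly underpowered.

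**Working it through.** **Inputs from the documents.** 40 analysable per group for 80% power, significance level 0.05, common SD of 38 percentage points of CPD reduction, and 10% attrition (C8 and SAP). The variance of the interaction is four times that of the main effect (C8). 45 per cell (C5a). 200 recruited and 180 completing (C3). 180 in total and 15 per group (section 1.1).

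**Assumptions.** The test is two-sided; the text does not say. The text gives no numeric effect size, and Figures 3a and 3b, which illustrate the hypothesised effect, were not available in the copy reviewed. The effect is therefore back-solved from the stated 80%.

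**Step 1: reproduce the plan's own figure.** 40/(1 − 0.10) = 44.4, rounded up to 45 per group, and 4 × 45 = 180. This matches C8 and the SAP. (Multiplying instead, 40 × 1.10 = 44 per group or 176 in total, comes close but is not the figure stated.)

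**Step 2: test the 15.** 4 × 15 = 60, not 180. From the total, 180/4 = 45, which agrees with C5a, C8 and the SAP.

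**Step 3: test the two uses of 180.**

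| Reading | Randomised or recruited | Completing | Completing per group |
|---|---|---|---|
| C8 and SAP | 180 | 180 × 0.9 = 162 | 40.5 |
| C3 | 200 | 180 | 45 |

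C3 states no attrition rate, but 180/0.9 = 200 exactly. That is why it looks like the same 10% applied again to a number that already contains it.

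**Step 4: effect implied by the power claim.** With n per group, the interaction contrast (difference of the two simple effects) has SE = 38 × √(4/n), and the main effect has SE = 38 × √(1/n). The variance ratio is 4, as C8 says. At n = 40 the contrast SE is 12.02. The contrast detectable with 80% power is (1.96 + 0.8416) × 12.02 = 33.7 points, or about 16.8 points for concentration at each power level, reversed in sign. The noncentral t version gives 33.9, or about 16.9 per simple effect.

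**Step 5: power at each candidate group size.** Under the normal approximation, power ≈ Φ(33.7/SE − 1.96). The third column uses the noncentral t with its own back-solved contrast of 33.9. The last column uses the noncentral t over assumed simple effects of 15 and 20 points, chosen only to bracket the back-solved value.

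| Analysable per group | Normal | Noncentral t | Range for 15 to 20 points |
|---|---|---|---|
| 15 | 0.404 | 0.396 | 0.324 to 0.517 |
| 40 | 0.800 | 0.800 | not computed |
| 40.5 | 0.805 | 0.805 | 0.704 to 0.915 |
| 45 | 0.844 | 0.845 | 0.750 to 0.940 |

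**The case against.** The 15 is isolated. Its own paragraph gives 180, every other section gives 45 per group or 180, the SAP is internally consistent, and no analysis rests on 15. A reader can see what was meant, so its 40% power describes a trial nobody intends to run. That is fair: the figure shows what the literal text would imply, not a real risk.

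On 180 versus 200, C3 openly says it raised the number and why. It gives no rate, so a second 10% allowance is an inference. There is also a stage at which people can be lost before randomisation: participants consent, are then screened in person with breath CO and, for women, a pregnancy test, and only then are randomised. On that view 200 might be consented and 180 randomised. This is plausible, but C3 does not say it. C3 says 180 complete the study, which conflicts with 180 randomised less attrition. The ambiguity is a reason to define the term.

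The power figures at 40.5 and 45 per group follow from the 80% claim and are no independent check on it. That also stands. They show only that neither 180-based reading endangers the claim.

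**Conclusion.** Both inconsistencies are real and should be fixed. The number randomised per group is given as 15 or 45 (60 or 180 in total). The pair randomised or recruited / completing is 180 / about 160 in C8 and the SAP, against 200 / 180 in C3. The sample-size derivation supports 45 per group and 180 randomised, and it reproduces.

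The stated 80% power is not undermined, since either 180-based reading leaves at least 40 analysable per group. The issue is consistency in basic design figures, not a power shortfall. The contradictions in the counts rest on the text alone. The power figures rest on an assumed two-sided test, the stated SD of 38 and an effect back-solved from the plan's own claim. That the 200 reflects a repeated 10% allowance is likely but not stated.

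**What to change.** 1. In section 1.1, replace 15 with the planned number randomised per group.
2. In C3, say whether recruited means consented or randomised.
3. State one number randomised and one number expected to be analysable, overall and per group, and use them throughout:
   - **If 180 are randomised:** keep 45 per group and the 80% power statement. Correct C3 to 180 randomised with about 160 expected to complete. If 200 is the number to be consented, C3 can say so.
   - **If 200 are randomised and 180 complete:** change 45 to 50 randomised per group in C5a, C8 and the SAP, and use 50 in section 1.1. Update 180 wherever it means randomised, including section 1.1, the Abstract and the Specific Aims. Restate power for 45 analysable per group, about 84% at the same effect.

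The cost is wording only, with no change to the analysis. The second option randomises 20 more people than C8 and the SAP state, but no more than C3 already plans to recruit.
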